### **Aim of the work:**

The purpose of this study is to assess the outcomes and efficacy of ejaculatory preserving TURP in terms of voiding, erectile function, and ejaculation.

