**Surgical Technique:**

Cystoscopy will be conducted under spinal anaesthesia with a 30° telescope and the patient in dorsal lithotomy posture. Eligible patients will be randomly assigned to one of two groups with double blind evaluation. Group 1 will have ejaculatory preserving TURP, whereas Group 2 will

have traditional TURP. Randomization will be done by computer programming such as SAS. The Operators will be the supervisors of the principle investigator.

All procedures will be carried out with bipolar-flow 26 Fr bipolar resectoscopes (Karl-Storz, Germany) configured for resection in 0.9% saline solution and cut/coagulation set at 130/70 W.

In Group 1, resection of lateral lobes to the capsule and the ventral side to the level of the verumontanum with avoidance of paracollicular digging. Circular resection of the internal bladder neck will be done. Then the next step will be apical resection utilizing the colliculus seminalis as a distal resection border and maintaining a 1 cm safety area for preservation of ejaculation.

In Group 2, the whole adenoma tissue, including the tissue in front of the verumontanum and bladder neck, will be removed to the prostatic capsule.

After full hemostasis, a 20 Fr three-way catheter will be placed into the bladder, traction will be performed, and the bladder will be irrigated with 0.9% saline postoperatively until clear effluent is seen.

The patient will be discharged from the hospital on the next postoperative day. Sexual activity will be prohibited for 6 weeks following the intervention.

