#### **Follow up:**

All patients will be followed-up regularly at 3 and 6 months postoperatively with the IPSS, Qmax, PVR, IIEF-5Q, MSHQ-EjD Short Form, and rates of complications (including urethral stricture, incontinence, bladder neck contracture, Recatheterisation, UTI, and retrograde ejaculation).

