**Statistical analysis:**

Statistical analysis was done by SPSS v26 (IBM Inc., Chicago, IL, USA). Shapiro-Wilks test and histograms were used to evaluate the normality of the distribution of data. Quantitative parametric variables were presented as mean and standard deviation (SD) and compared between the two groups utilizing unpaired Student's T- test. Quantitative non-parametric data were presented as median and interquartile range (IQR) and were analyzed by Mann-Whitney test. Qualitative variables were presented as frequency and percentage and were analyzed utilizing the Chi-square test or Fisher's exact test when appropriate. A two tailed P value  $< 0.05$  was considered statistically significant

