## Results

In this study, 103 patients were assessed for eligibility; 8 patients did not meet the criteria and 5 patients refused to participate in the study. The remaining patients were randomly allocated into two equal groups (45 patients in each). All allocated patients were followed-up and analyzed statistically (**Figure 42**).

[figure not shown]

[figure not shown]
Figure 1: CONSORT flow chart of the enrolled patients.

[figure not shown]

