**Table 7: PVR (ml) and Qmax (ml/sec) of the studied groups**

		Group 1 (n=43)	Group 2 (n=41)	P value	Mean difference (95% CI)
PVR (mL)	Preoperative	356 (250-380)	340 (289-391)	0.345	14(-20:48)
	3 months postoperative	55 (43.5-68.5)	39 (29-52)	0.003*	-13(-22: -4)
	6 months postoperative	49 (42.5-72)	34(22-47)	<0.001*	-21(-29: -12)
Qmax (mL/sec)	Preoperative	4.92±1.73	4.5±1.88	0.270	0.42(-0.334: 1.178)
	3 months postoperative	19.04±4.77	21.73±4.63	0.01*	-2.696(-4.738: -0.654)
	6 months postoperative	18.78±5.16	19.71±6.22	0.457	-0.93(-3.407: 1.55)

[figure not shown]
\*Significantly different as P value  $\leq 0.05$ , PVR: Postvoid residual, Qmax: Maximum urinary flow rate, CI: Confidence interval

PVR was insignificantly different at preoperative between both groups and was significantly higher at (3 months and 6 months) postoperative in group 1 than group 2 as (P value =0.003 and <0.001 respectively).

Qmax was significantly lower at 3 months postoperative in group 1 than group 2 as (P value =0.03) and was insignificantly different at (preoperative and 6 months postoperative) between both groups.

**Figure 12:** PVR of the studied groups.

**Figure 13:** Qmax of the studied groups.

[figure not shown]

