**Table 8: Intraoperative factors of the studied groups**

		Group 1 (n=45)	Group 2 (n=45)	P value	Mean difference or RR (95% CI)
Operative time (min)	Mean <math>\pm</math> SD	33.51 $\pm$ 11.49	40.53 $\pm$ 14.64	0.013*	-3.42(-11.15: 4.31)
	Range	15 – 60	18 – 75		
Blood transfusion		1 (2.22%)	2 (4.44%)	1	0.49(0.04:5.59)

[figure not shown]
\*Significantly different as P value  $\leq$ 0.05, CI: Confidence interval, RR: Relative risk

Operative time was significantly lower in group 1 than group 2 as (P value =0.013).

Blood transfusion was insignificantly different between both groups.

**Figure 14:** Operative time of the studied groups.

[figure not shown]
**Figure 15:** Blood transfusion of the studied groups.

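### No primary outcome or multiplicity rule: ten of 24 between-arm outcome tests are called significant without family-wise error control, and under Holm four hold, two are borderline and four do not

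*Combined protocol and SAP*

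**What the plan says.** The Aim of the work is to "assess the outcomes and efficacy of ejaculatory preserving TURP in terms of voiding, erectile function, and ejaculation": three domains, unranked. The Follow up section sets the schedule: "All patients will be followed-up regularly at 3 and 6 months postoperatively with the IPSS, Qmax, PVR, IIEF-5Q, MSHQ-EjD Short Form". It adds complication rates, retrograde ejaculation among them. No outcome and no visit is marked as primary.

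The Statistical analysis section names the tests and closes with a single criterion: "A two tailed P value" below 0.05 "was considered statistically significant". It contains no hierarchy, no multiplicity adjustment and no sample-size basis. It is written in the past tense and the results follow it in the same document.

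The results apply the criterion test by test. Under Table 7: "Qmax was significantly lower at 3 months postoperative in group 1 than group 2". Under Table 8: "Operative time was significantly lower in group 1 than group 2 as (P value =0.013". Both are worded in the same way as the preserved-ejaculation result under Table 10.

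**The concern.** With several outcomes, two visits and one unadjusted threshold, the plan cannot say which result answers the trial's question or how many significant findings to expect by chance.

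This matters here because the ten results point both ways. Preserved ejaculation (two visits), IIEF-5Q (two visits) and operative time favour Group 1. PVR (two visits), 3-month Qmax and sperm concentration (two visits) favour Group 2. Without a stated order, either message could be put first after seeing the data. Isolated findings also gain the same standing as the main one: Qmax differs at 3 months but not at 6 (P=0.457). Sperm concentration is declared significant although semen measures are not in the Follow up list.

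**Working it through.** **Counting the tests.** Post-randomisation between-arm P values in Tables 2-5 and 7-10: IPSS 2, IIEF-5Q 2, MSHQ-EjD 2, postoperative laboratory 3, PVR 2, Qmax 2, operative time 1, transfusion 1, complications 3, preserved ejaculation 2, semen volume 2, sperm concentration 2; total 24. Ten are called significant. Tables 11-13 add 2 + 5 + 1 = 8. The six follow-up outcomes (IPSS, Qmax, PVR, IIEF-5Q, MSHQ-EjD, preserved ejaculation) at two visits make 12.

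**Reproducing the printed P values** (pooled t-test from tabulated means, SDs and n):
- Operative time: SE = √((11.49² + 14.64²)/45) = 2.774; difference 33.51 − 40.53 = −7.02; t = −2.53 on 88 df; P=0.0132, matching the printed 0.013. The 95% CI is −12.53 to −1.51. Table 8 instead prints −3.42 (−11.15 to 4.31), the same interval as prostate volume in Table 6.
- Qmax at 3 months: pooled SD = √((42×4.77² + 40×4.63²)/82) = 4.70; SE = 4.70×√(1/43 + 1/41) = 1.026; difference −2.69; P=0.0105. This agrees with 0.01 in Table 7, not with 0.03 in the text beneath it.
- IIEF-5Q: P=0.0025 (3 months) and 0.00097 (6 months).
- Preserved ejaculation, chi-square: 35/43 vs 8/41, P=1.4×10⁻⁸; 34/43 vs 8/41, P=4.8×10⁻⁸.
- MSHQ-EjD: the headed 43 vs 41 gives P=0.075 and 0.588. The printed 0.284 and 0.741 are matched closely only with 35 vs 8 (0.286) and 34 vs 8 (0.744), which are the numbers of men with preserved ejaculation.

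PVR and sperm concentration are taken as printed, with 6-month PVR as <0.001.

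**Holm adjustment.** Order the P values; the k-th smallest of m is multiplied by (m − k + 1), and adjusted values may not decrease.

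| Result | P | Holm, m=24 | Holm, m=12 |
|---|---|---|---|
| Preserved ejaculation, 3 and 6 months | 1.4×10⁻⁸, 4.8×10⁻⁸ | <0.00001 | <0.00001 |
| IIEF-5Q and PVR, 6 months | 0.00097, <0.001 | at most 22×0.001 = 0.022 | at most 10×0.001 = 0.010 |
| IIEF-5Q, 3 months | 0.00246 | ×20 = 0.049 | ×8 = 0.020 |
| PVR, 3 months | 0.003 | ×19 = 0.057 | ×7 = 0.021 |
| Sperm concentration, 6 months | 0.005 | ×18 = 0.09 | not in family |
| Qmax, 3 months | 0.0105 | ×17 = 0.18 | ×6 = 0.063 |
| Operative time | 0.0132 | ×16 = 0.21 | not in family |
| Sperm concentration, 3 months | 0.036 | ×15 = 0.54 | not in family |

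The two borderline rows depend on rounding. With the printed 0.003, 3-month IIEF-5Q becomes 20×0.003 = 0.06. A PVR P value anywhere from 0.0025 to 0.0035 gives 0.048 to 0.067 over 24.

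**Sensitivity of Qmax to the input errors.** With the 0.03 in the text, Holm over 12 is 6×0.03 = 0.18. If corrected MSHQ-EjD results fell below Qmax's P value at both visits, the multiplier would drop to 4 and give 0.042.

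**Benjamini-Hochberg over 24** (P×24/rank): 6-month sperm concentration 0.005×24/7 = 0.017; Qmax 0.0105×24/8 = 0.031; operative time 0.0132×24/9 = 0.035; 3-month sperm concentration 0.036×24/10 = 0.086.

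**Reference figure for chance findings.** 1 − 0.95¹² = 0.46 and 1 − 0.95²⁴ = 0.71, if every null hypothesis were true and all tests independent.

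**The case against.** The strongest reply is that each test keeps its own 5% level and that the main result survives any adjustment. Both are true. What is absent is control across the family, and a reader who infers that there is no error control at all, or that all ten results are doubtful, goes too far.

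A second reply is that the failures depend on the criterion chosen. This also stands in part. Over the 12 follow-up tests, 3-month IIEF-5Q and PVR pass Holm comfortably. Under Benjamini-Hochberg over 24, Qmax, operative time and 6-month sperm concentration pass as well. But the plan specifies neither procedure, and false-discovery control is a weaker claim than a confirmatory one.

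Three further inferences are tempting and should not be drawn:
- The 46% and 71% figures are not this trial's false-positive rate. They assume that all nulls are true, which the preserved-ejaculation result contradicts, and that the tests are independent, whereas correlation lowers the figure.
- The rule "Sexual activity will be prohibited for 6 weeks following the intervention" does not show that the 3-month visit observes only about half its interval. The documents give no recall window for the questionnaires, and the point has no bearing on Qmax or operative time.
- Naming 6-month preserved ejaculation as primary now would not repair the plan. It would give that status to one of the two smallest P values already printed and would read as pre-specification.

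**Conclusion.** The concern holds as a lack of family-wise control, and it should be corrected. Of the ten results called significant, four hold clearly over all 24 tests (preserved ejaculation at 3 and 6 months; IIEF-5Q and PVR at 6 months). Two are borderline over 24 and hold over 12 (IIEF-5Q and PVR at 3 months). Four do not hold (3-month Qmax, operative time, sperm concentration at both visits).

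A reader might infer that those four are false positives. The documents do not show that; they show only that the four cannot be presented as confirmatory. The sorting assumes Holm, the stated families, and the printed PVR and sperm-concentration P values. The 12-test result for Qmax is provisional until its own P value and the MSHQ-EjD denominators are settled.

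**What to change.** 1. **Correct the inputs first.** Reconcile the two Qmax P values in Table 7 and its text. Replace the operative-time interval in Table 8 (the summaries give −7.02, −12.53 to −1.51). State who was analysed for MSHQ-EjD and correct the headed n or the analysis. Define preserved ejaculation, which the Follow up section covers only through its complement, retrograde ejaculation, listed as a complication.
2. **Amend the Statistical analysis section.** Suggested text: *No primary outcome, primary visit or multiplicity rule was pre-specified. Holm-adjusted P values are reported over six follow-up outcomes (IPSS, Qmax, PVR, IIEF-5Q, MSHQ-EjD, preserved ejaculation) at 3 and 6 months, 12 tests. This family was chosen after the data were seen. Operative, laboratory, semen, complication and Tables 11 to 13 results are exploratory and are given with 95% confidence intervals and no statements of significance.* If the ethics-approved version names a primary outcome, cite it in place of the first sentence.
3. **Rewrite the result sentences.** Remove the significance wording for operative time, sperm concentration, and Tables 11 and 12. Remove it for 3-month Qmax too, unless the corrected inputs bring its adjusted P below 0.05.

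The cost is plan wording, a re-run of existing tests and edited result sentences; no new data are needed. The downside is that several printed significant results become exploratory or non-significant.

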## Results

In this study, 103 patients were assessed for eligibility; 8 patients did not meet the criteria and 5 patients refused to participate in the study. The remaining patients were randomly allocated into two equal groups (45 patients in each). All allocated patients were followed-up and analyzed statistically (**Figure 42**).

[figure not shown]

[figure not shown]
Figure 1: CONSORT flow chart of the enrolled patients.

[figure not shown]

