**-Type of the study:**

A prospective comparative study.

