**Table 2: IPSS score of the studied groups**

	Group 1 (n=43)	Group 2 (n=41)	P value	Mean difference (95% CI)
Preoperative (0-35)	26.58±3.65	28.42±3.2	0.013*	-1.84(-3.28: -0.406)
3 months postoperative	7.14±2.99	6.68±2.43	0.446	0.456(-0.729: 1.642)
6 months postoperative	5.12±2.62	4.07±3.38	0.117	1.043(-0.265:2.352)

\*Significantly different as P value  $\leq 0.05$ , CI: Confidence interval, IPSS: International prostate symptom Score

IPSS score was significantly lower at preoperative (0-35) in group 1 than group 2 as (P value = 0.013) and was insignificantly different at (3 and 6 months) postoperative between both groups.

[figure not shown]

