**Figure 5: IIEF-5Q of the studied groups.**

**Table 4: MSHQ-EjD score of the studied groups**

	Group 1 (n=43)	Group 2 (n=41)	P value	Mean difference (95% CI)
Preoperative (1-15)	12.42±1.23	10.98±2.16	<0.001*	1.44(0.708: 2.181)
3 months postoperative	10.26±1.42	9.63±1.77	0.284	0.632(-0.544: 1.808)
6 months postoperative	10.62±1.76	10.38±2.26	0.741	0.243(-1.232: 1.717)

\*Significantly different as P value  $\leq 0.05$ , CI: Confidence interval, MSHQ-EjD: Male sexual health questionnaire – ejaculatory dysfunction short form, TTT: Treatment

MSHQ-EjD score was significantly higher at preoperative (1-15) in group 1 than group 2 (P value <0.001) and was insignificantly different at three and six months postoperative between both groups.

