**Table 5: Laboratory investigation of the studied groups**

[figure not shown]
		Group 1 (n=45)	Group 2 (n=45)	P value	Mean difference (95% CI)
Hemoglobin (g/dL)	Preoperative	13.34±1.85	13.88±1.35	0.121	-0.535(-1.21: 0.145)
	Postoperative	12.29±1.73	12.55±1.58	0.466	-0.256(-949: 0.438)
WBC (10^9/L)	Preoperative	8.23±3.27	8.1±2.88	0.842	0.13(-1.161: 1.42)
	Postoperative	10.18±2.09	10.55±3.22	0.524	-0.366(-1.50:0.772)
Creatinine (mg/dL)	Preoperative	1.18±0.41	1.07±0.36	0.195	0.106(-0.055: 0.267)
	Postoperative	1.11±0.24	1.1±0.33	0.874	0.009(-0.112: 0.132)
Total PSA (ng/mL)	Median	2.13	4.2	0.001*	1.41(0.60: 2.30)
	IQR	1.39 - 3.8	2.6 - 5.3		

\*Significantly different as P value  $\leq 0.05$ , WBC: White blood cell, CI: Confidence interval, PSA: Prostate-specific antigen

[figure not shown]
Hemoglobin, WBC and creatinine were insignificantly different at preoperative and postoperative between both groups.

Total PSA was significantly lower in group 1 than group 2 as (P value =0.001).

[figure not shown]

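### Three of 14 baseline comparisons are imbalanced to a degree unusual under random allocation, and no analysis adjusts for them: check the data, document the allocation and add adjusted estimates

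*Combined protocol and SAP*

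**What the plan says.** The Surgical Technique section sets out the plan: "Eligible patients will be randomly assigned to one of two groups with double blind evaluation". On method it says only: "Randomization will be done by computer programming such as SAS". It gives no sequence type, block size, stratification or concealment, and the timing of assignment can only be guessed from the sentence's position after the one on cystoscopy. The Results section then reports: "The remaining patients were randomly allocated into two equal groups (45 patients in each". The design label under Type of the study is "A prospective comparative study".

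The tables report three baseline imbalances, each without further comment:

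- Table 2: "IPSS score was significantly lower at preoperative (0-35) in group 1 than group 2 as (P value = 0.013".
- Table 4: "MSHQ-EjD score was significantly higher at preoperative (1-15) in group 1 than group 2 (P value <0.001".
- Table 5: "Total PSA was significantly lower in group 1 than group 2 as (P value =0.001".

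The Statistical analysis section compares groups by t-test, Mann-Whitney, chi-square or Fisher's exact test, two-sided at 0.05. It contains no adjustment for any baseline value.

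**The concern.** If allocation was random and the tables are right, baseline differences arise by chance alone, so a cluster of small baseline P values bears on the allocation process or on the data. The smallest one is for ejaculatory function, the domain that the modified technique is meant to protect.

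Two things are at stake. First, the between-group results in Tables 2 to 10 are unadjusted, so any imbalance in a variable related to an outcome passes straight into the comparison. Secondly, the one-line description of the method gives a reader no means of judging whether assignments could be foreseen. Where effects are modest, part of the difference could then reflect who entered each arm.

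**Working it through.** **Inputs.** There are 14 baseline comparisons: age, diabetes, hypertension and ischaemic heart disease (Table 1), IPSS (Table 2), IIEF-5Q (Table 3), MSHQ-EjD (Table 4), haemoglobin, WBC, creatinine and PSA (Table 5), prostate volume (Table 6), PVR and Qmax (Table 7).

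**Step 1: reproduce the printed P values.** Pooled t-test at 45 per arm, SE = s × √(2/45).

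- IPSS: 26.58 ± 3.65 v 28.42 ± 3.2. s = √[(3.65² + 3.2²)/2] = 3.43; SE = 0.724; t = −1.84/0.724 = −2.54; P = 0.0127 (printed 0.013).
- MSHQ-EjD: 12.42 ± 1.23 v 10.98 ± 2.16. s = 1.76; SE = 0.371; t = 1.44/0.371 = 3.89; P = 0.0002 (printed <0.001).
- PSA: the rank test cannot be rerun without patient data. From the printed 1.41 (0.60 to 2.30), SE = 1.70/3.92 = 0.434; z = 3.25; P = 0.0011 (printed 0.001).

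Tables 2 and 4 are headed 43 and 41, but their preoperative intervals fit 45 and 45. For IPSS, 45/45 gives −3.28 to −0.40 and 43/41 gives −3.33 to −0.35; the table prints −3.28 to −0.406. At 43/41 the P values would be 0.016 and 0.0003, so nothing turns on this. Prostate volume has no readable P value; its interval implies about 0.38.

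**Step 2: allow for 14 comparisons.** Bonferroni holds under any dependence and needs no cut-off chosen from the data.

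- MSHQ-EjD: 14 × 0.000197 = 0.003.
- PSA: 14 × 0.001 = 0.014, or 14 × 0.00115 = 0.016.
- IPSS: 14 × 0.013 = 0.18, which does not survive.

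**Step 3: chance of three or more at the document's own 0.05 level.** With independent variables, 1 − 0.95¹⁴ − 14(0.05)(0.95¹³) − 91(0.05²)(0.95¹²) = 1 − 0.488 − 0.359 − 0.123 = 0.030. The true correlation is not given. Simulation with an assumed common correlation gives 0.035 at 0.1, 0.047 at 0.2, 0.060 at 0.3 and 0.081 at 0.5.

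**Step 4: which outcomes are exposed.**

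- Preserved ejaculation at 6 months: RR = (34/43)/(8/41) = 0.791/0.195 = 4.05, 95% CI 2.14 to 7.69. (Table 10 prints 15.58 under an RR heading; that is the odds ratio, 34 × 33/(9 × 8).) The E-value, RR + √[RR(RR − 1)], is 7.6, and 3.7 at the lower limit.
- IIEF-5Q at 6 months: difference 2.27 points. Converting by RR ≈ exp(0.91d) gives an E-value of about 3.4, and 2.0 at the lower limit.
- Operative time: 40.53 − 33.51 = 7.02 minutes; E-value about 2.6, and 1.5 at the lower limit.
- PVR (55 v 39 mL at 3 months, 49 v 34 at 6) and 3-month Qmax (19.04 v 21.73 mL/s) are worse in Group 1.

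**Step 5: signs of reporting error.** Tables 6 and 8 print the same difference and interval, −3.42 (−11.15 to 4.31), for prostate volume and operative time, although the operative-time means differ by 7.02. For 3-month Qmax, Table 7 gives P = 0.01 and the text below it 0.03.

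**The case against.** Randomised trials do produce imbalances, and no baseline test can prove that allocation was not random. That stands. A reader might infer from these tables that men were steered to an arm, or that the word randomised must go. The documents do not support either step:

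- The design label and the neutral wording under Study Population do not contradict the explicit statement of randomisation under Surgical Technique. Assignment late in the process is not evidence of steering; it can reduce selection.
- The PSA medians (2.13 v 4.2) lie either side of 4 ng/mL, but the inclusion criteria admit higher values with biopsy-proven BPH, so this says nothing about allocation.
- The direction is uniform only among the three significant variables. Diabetes (9 v 7), ischaemic heart disease (2 v 0), creatinine (1.18 v 1.07) and haemoglobin (13.34 v 13.88) lean against Group 1.
- One can reach odds of about 1 in 80,000 by asking for two P values at or below 0.001 and three at or below 0.013. That takes the cut-offs from the data and assumes independence; at an assumed correlation of 0.4 it is about 1 in 1,000. The 3% to 8% figure and the Bonferroni results are the fair summary.
- IIEF-5Q was balanced at entry (19.76 v 20.04, P = 0.592), so adjusting for its own baseline alone would not be expected to shrink the later gap.
- Reporting error is a live alternative, given the slips in Step 5.

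What survives is narrower. Two imbalances remain after a correction that needs no assumption about dependence, the allocation method is barely described, and no estimate is adjusted.

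**Conclusion.** The concern holds in a limited form. The baseline pattern is unusual under the stated random allocation: MSHQ-EjD and PSA remain significant after correction for 14 comparisons, and three or more below 0.05 has a probability of 3% to about 8%, depending on an assumed correlation of 0 to 0.5. It does not establish non-random allocation, and error in the tables has to be excluded first.

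The consequences differ by outcome. The preserved-ejaculation result is too large to be plausibly explained by these imbalances. The IIEF-5Q and operative-time differences are more exposed, though not defenceless. The PVR and 3-month Qmax differences go against Group 1, so selection of easier cases into that group would tend to mask them, not create them. These readings rest on the printed summary statistics, on 45 per arm at baseline, and on the normal approximation for PSA.

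**What to change.** 1. Check the baseline values in Tables 2, 4 and 5 against source data, correct any errors, and head the baseline rows with the number of men they describe.
2. Compare the allocation list with the treatment given for all 90 men. Report the sequence type, any blocking, the concealment, the timing of assignment and the number of mismatches. A match alone is not enough, because a predictable or unconcealed sequence can also match. Blocking is worth asking about: an exact 45/45 split has only an 8.4% chance under simple randomisation. If random allocation cannot be substantiated, say so and qualify the statement in the Results; a missing list would not in itself prove that allocation was not random.
3. Whatever the check shows, report adjusted beside unadjusted estimates for preserved ejaculation, IIEF-5Q, PVR, Qmax and operative time. Adjust for the outcome's own baseline value where one exists, plus age, log PSA, preoperative IPSS, preoperative MSHQ-EjD and prostate volume. For preserved ejaculation use few covariates or a penalised model: at 6 months there are 34 + 8 = 42 events, or 7 per term with treatment and five covariates. State that the adjustment was decided after the data were seen.

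The cost is a document check and a few regressions on data already held. The downside is that the design label may have to be weakened.
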